5. Patients who test positive for tetrahydrocannabinol (THC) or non-approved cannabidiol (CBD) via plasma drug screen.
6. Chronic use of oral steroid medications, ketoconazole (except for topical formulations), St. John's Wort, or other IPs is not permitted.
7. Adrenocorticotropic hormone (ACTH), prednisone, or other systemically administered (non-inhaled) steroids must be discontinued \geq 28 days prior to screening. Concomitant topical, inhaled or intranasal steroids are allowed and do not warrant exclusion from the study.

IND 044,020
Protocol 1042-TSC-2001Marinus Pharmaceuticals, Inc.
11 Jun 2021

8. Changes in any chronic medications within the month (e.g., 30 days) prior to the screening visit. All concomitant medications must have been at a stable in dose for at least 1-month prior to the screening visit unless otherwise noted.
9. Patient is being considered for epilepsy surgery or has undergone surgery for epilepsy within the 6 months prior to screening.
10. Have an active CNS infection, demyelinating disease, degenerative neurological disease, or CNS disease deemed progressive. This includes tumor growth which in the opinion of the investigator could affect primary seizure control.
11. Have any disease or condition (medical or surgical; other than TSC) at the screening visit that might compromise the hematologic, cardiovascular, pulmonary, renal, gastrointestinal, or hepatic systems; or other conditions that might interfere with the absorption, distribution, metabolism, or excretion of the IP, or would place the patient at increased risk. This may include any illness in the past 4 weeks which in the opinion of the investigator may affect seizure frequency.
12. An aspartate aminotransferase (AST/serum glutamic oxaloacetic transaminase [SGOT]) or alanine aminotransferase (ALT/serum glutamic pyruvic transaminase [SGPT]) $> 3 \times$ the upper limit of normal (ULN) at screening or baseline visits and confirmed by a repeat test.
13. Total bilirubin levels $> 1.5 \times$ ULN at screening or baseline visit and confirmed by a repeat test. In cases of documented, stable medical condition (i.e., Gilbert's Syndrome) resulting in levels of total bilirubin $>$ ULN, the medical monitor can determine if a protocol exception can be made.

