-4 (Screening Visit – Start of Baseline)	0 (Baseline Treatment Visit)	Day 1	Day 2	Day 3	1	2, 3, 4	5	9	12	16 Taper/Safety Visits ^p	
Visit Windows	+ 4 days			± 1 day	± 3 days	± 3 days	± 3 days	± 3 days	± 3 days	± 3 days	
VISIT	Visit 1 ^a	Visit 2 ^o	Phone Follow-up	Phone Follow-up	Phone Follow-up	Visit 3	Phone Follow-up	Visit 4	Phone Follow-up	Visit 5	Visit 5a
a.	Patient rescreening is allowed as agreed by the sponsor and the investigator unless there is a general concern for patient safety or an inability for the patient to become eligible (e.g., GNX allergy, sensitivity or exposure, non-TSC and/or other ineligible epilepsy, chronic prohibited medical condition or treatment). Subsequent screening should take place at least 30 days from the patient's last visit.										
b.	Written informed consent/assent must be obtained from patient, parent or LAR before any study assessments are performed. Pediatric assent should be obtained, if appropriate.										
c.	Previous genetic testing results will be accepted and reviewed to assess if a pathogenic TSC1 or TSC2 variant is present. If genetic testing has not previously been performed, then a biological sample will be obtained to complete genetic testing at the sponsor's designated lab. Note: TSC diagnosis does not require pathogenic TSC1 or TSC2 mutations if the clinical criteria are met.										
d.	Height and weight will be measured. Length will be measured if height cannot be obtained.										
e.	Only weight will be measured. At each visit, dosing will be reviewed and adjusted as needed based on a patient's current weight.										
f.	Chemistry and Hematology.										
g.	An attempt should be made to collect a urine sample for a urinalysis at screening; otherwise, the urine sample can be collected at baseline for the urinalysis if possible.										
h.	A drug screen (plasma) will be performed to test for THC and CBD at screening. If the screening drug test is positive, the patient can be retested, via plasma, after two weeks. A positive drug test during the treatment period will result in early termination.										
i.	Serum pregnancy test is required for all girls/women of childbearing potential.										
j.	Population PK will be conducted at these visits (Visit 4: between 1-5 hours since last IP dosing, Visit 5: between 4-8 hours since the last IP dosing).										

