4.2. Exclusion Criteria (Part A)

Patients are excluded from the study if any of the following criteria apply:

1. Previous exposure to GNX.
2. Pregnant or breastfeeding.
3. Concurrent use of strong inducers or inhibitors of cytochrome P450 (CYP)3A4/5/7. Any strong inhibitor or inducer of CYP3A4/5/7 must be discontinued at least 28 days before Visit 2, study drug initiation. This does not include approved ASMs.
4. Patients who have been taking felbamate for less than 1 year prior to screening.
5. Patients who test positive for tetrahydrocannabinol (THC) or non-approved CBD via plasma drug screen.

6. Chronic use of oral steroid medications, ketoconazole (except for topical formulations), St. John's Wort, or other IPs is not permitted.
7. Adrenocorticotrophic hormone (ACTH), prednisone, or other systemically administered (non-inhaled) steroids must be discontinued > 28 days prior to screening. Concomitant topical, inhaled or intranasal steroids are allowed and do not warrant exclusion from the study.
8. Changes in any chronic medications within the month (e.g., 30 days) prior to the screening visit. All concomitant medications must have been at a stable in dose for at least 1-month prior to the screening visit unless otherwise noted.
9. Patient is being considered for epilepsy surgery or has undergone surgery for epilepsy within the 6 months prior to screening.
10. Have an active CNS infection, demyelinating disease, degenerative neurological disease, or CNS disease deemed progressive. This includes tumor growth which in the opinion of the investigator could affect primary seizure control.
11. Have any disease or condition (medical or surgical; other than TSC) at the screening visit that might compromise the hematologic, cardiovascular, pulmonary, renal, gastrointestinal, or hepatic systems; or other conditions that might interfere with the absorption, distribution, metabolism, or excretion of the IP, or would place the patient at increased risk. This may include any illness in the past 4 weeks which in the opinion of the investigator may affect seizure frequency.
12. An AST/serum glutamic oxaloacetic transaminase (SGOT) or ALT/serum glutamic pyruvic transaminase (SGPT) $> 3 \times$ the ULN at screening or baseline visits and confirmed by a repeat test.

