5.2.1. Concomitant AED Medications

Patients in the study should be on a stable regimen of AED medications at therapeutic doses for \geq 1 month prior to the screening visit, and cannot be changed at any time prior to Visit 5 during Part A, but may be adjusted during Part B.

Vagus nerve stimulator, ketogenic diet, and modified Atkins diet should be unchanged for 3 months prior to screening and will not count towards the number of ASMs.

Patient with surgically implanted VNS will be allowed to enter the study provided that all of the following conditions are met:

- The VNS has been in place for \geq 1 year prior to the screening visit.
- The settings must have remained constant for 3 months prior to the screening visit and remain constant throughout the baseline and Part A.
- The battery is expected to last for the duration of the baseline and Part A.

The use of felbamate is allowed provided that the patient has been maintained on a stable dose of felbamate for at least 1 year, and has had stable liver function (AST/ALT) and hematology during the course of treatment, and is expected to remain constant throughout the 12-week treatment period.

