5.4. Excluded Medications

Excluded medications include all steroid medications, other IPs, as well as ketoconazole, and St. John's wort. Concurrent use of ACTH, prednisone or other glucocorticoid is not permitted, nor use of moderate or strong inducers or inhibitors of CYP3A4/5/7. Patients on ACTH, prednisone, or other systemically (non-inhaled) administered steroids should be off the product greater than 28 days prior to screening. Any strong inhibitor or inducer of CYP3A4/5/7 must be discontinued at least 28 days before Visit 2, study drug initiation. A list of CYP3A4/5/7 inhibitors and inducers is included in Section 12.1. Concomitant topical and intranasal steroids for dermatologic reactions and allergic rhinitis are allowed as needed and do not warrant exclusion from the study.

Products containing THC or non-approved CBD are excluded in the treatment period (Part A) of the study but allowed in the OLE period (Part B). Tetrahydrocannabinol or non-approved CBD should be washed out for at least 6 weeks. Patients with a positive result on THC at the

screening and baseline visit will be excluded. Patients with a positive result on CBD without a prescription for an approved CBD would also be excluded.

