7.4.2. Drug Screen

A drug screen (plasma) will be performed to test for THC and non-approved CBD at Visit 1 (screening). If the screening drug test is positive, a confirmatory retest, via plasma, will be performed after 2 weeks. A positive drug test during the treatment phase will result in early termination.

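### Table 1 footnote h orders early termination for any positive on-treatment THC/CBD screen and omits the approved-CBD exemption given in exclusion 5 and Section 5.4 (minor)

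*Protocol*

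**What the plan says.** **The termination rule.** Footnote h to Protocol Table 1 is attached to the drug-screen row. It names the analytes as THC and CBD, allows a retest two weeks after a positive screening result, and ends: "A positive drug test during the treatment period will result in early termination". SAP Appendix A carries the same footnote. Section 7.4.2 has nearly the same sentence: "A positive drug test during the treatment phase will result in early termination". However, Section 7.4.2 opens by describing the Visit 1 screen as one for THC and non-approved CBD.

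**The exemption.** Exclusion criterion 5 in Section 4.2 covers "Patients who test positive for tetrahydrocannabinol (THC) or non-approved CBD via plasma drug screen", and the synopsis version matches it. Section 5.4 sets the product rule: "Products containing THC or non-approved CBD are excluded in the treatment period (Part A) of the study but allowed in the OLE period". It then says how to treat a CBD result: "Patients with a positive result on CBD without a prescription for an approved CBD would also be excluded".

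**Background treatment.** Under Section 5.2.1, concomitant antiepileptic medication "cannot be changed at any time prior to Visit 5 during Part A".

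**The on-treatment screen.** Section 7.2.6 schedules a plasma screen at Visit 5 (Week 12) for THC and CBD, with no approved/non-approved distinction. Appendix 2 lists the test in the same way.

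**The concern.** The eligibility rules and the termination rule use different definitions of a disqualifying result. Eligibility depends on the result together with the prescription. Termination, as footnote h words it, depends on the result alone. A patient can therefore be properly enrolled, change nothing, and still meet the termination rule.

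The case is foreseeable. Section 1.1 of the protocol names a branded cannabidiol product as having reduced seizures in a randomized trial, and Section 5.4 expressly provides for patients who hold a prescription for approved CBD.

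What is at stake is individual treatment. Visit 5 is the last Part A visit and also the visit at which Part B entry is confirmed. Termination there would mean stopping ganaxolone, a two-week taper under Section 4.5, and possible loss of the extension, all because of a product the protocol allows. A site that keeps the patient departs from footnote h. A site that terminates goes against Section 5.4.

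**Working it through.** The plan gives no figure to reproduce, so the check is a comparison of the texts.

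**1. What counts against the patient in each place**

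| Place | Trigger | Approved-CBD exemption |
|---|---|---|
| Exclusion 5 (synopsis and Section 4.2) | THC, or non-approved CBD, on plasma screen | Yes |
| Section 5.4, product rule | THC or non-approved CBD products, Part A treatment period | Yes |
| Section 5.4, result rule | CBD-positive with no prescription for approved CBD | Yes |
| Table 1 footnote h | Any positive drug test in the treatment period; analytes THC and CBD | No |
| SAP Appendix A, footnote h | Same as footnote h (a reproduction) | No |
| Section 7.4.2 | Any positive drug test in the treatment phase | Not in that sentence; can be inferred from the section's opening words about Visit 1 |

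**2. When the rule can apply.** Table 1 schedules Part A drug screens at Visits 1, 2 and 5, which is 3 screens. Visit 1 precedes dosing, and Section 7.2.2 places the Visit 2 procedures before ganaxolone is given. On-treatment screens in Part A: 3 − 2 = 1, at Visit 5 (Week 12).

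**3. Following one permitted patient through.**
- At entry the patient takes a stable, prescribed, approved CBD product. Exclusion 5 and Section 5.4 let the patient in.
- Section 5.2.1 keeps background antiepileptic treatment unchanged until Visit 5, and inclusion criterion 7 requires that no dosing change is foreseen during Part A. The patient is therefore expected still to be taking CBD at Week 12.
- The Week 12 screen looks for CBD, so a positive result is expected.
- Footnote h, taken literally, then terminates the patient, and Section 4.5 calls for the two-week taper.

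**4. Part B.** The Part B inclusion criterion (Section 4.1.1) is a seizure reduction of at least 35%. The exclusion criterion (Section 4.2.1) is a medical condition that makes ganaxolone unsafe. Neither mentions the drug screen, and Section 5.4 allows even THC and non-approved CBD in Part B. The literal rule could thus remove a patient whom the Part B criteria would admit.

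**5. Primary endpoint.** The only on-treatment Part A screen falls at the end of the 12 weeks over which seizures are counted. SAP Section 4.2.1.1 keeps all available Part A seizure data for ITT patients whether or not they stopped ganaxolone. No effect on the endpoint follows.

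**The case against.** The strongest reply is that the protocol, read as a whole, already answers the question. Exclusion 5 defines a relevant positive as THC or non-approved CBD on the plasma screen. The CBD sentence in Section 5.4 is not tied to a visit, unlike the THC sentence before it, so it can be read to cover Week 12. Section 4.5.1 lets the investigator withdraw a patient who needs a disallowed medication, and approved CBD is not one. Any site that enrolled such a patient has already applied the prescription test at Visits 1 and 2. On this view footnote h is shorthand.

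Much of this stands. It makes the intent fairly clear and keeps the point minor. It does not repair the footnote, which names CBD without qualification, uses mandatory language and sits on the schedule row that sites work from. The Section 5.4 sentence also follows directly on a rule about screening and baseline, so its reach to Week 12 has to be inferred.

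A reader might also infer that the same error occurs independently in three places. The documents do not support that. SAP Section 1.3.1 says its appendices reproduce the protocol's schedules. Section 7.4.2 introduces the screen as one for non-approved CBD; although those words refer to Visit 1, the exemption can reasonably be carried over. Only footnote h is plainly defective.

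**Conclusion.** The point holds and is minor. Footnote h, as written, contradicts exclusion 5 and Section 5.4 and gives the wrong result for a permitted patient at Week 12. The SAP copy inherits the wording. Section 7.4.2 needs the change only for consistency.

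The number affected cannot be estimated: the documents give no figure for approved-CBD use, and sites may follow Section 5.4, so it may be zero.

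The conclusion assumes that prescribed, approved CBD is treated as background antiepileptic medication under Section 5.2.1, that a patient taking it tests positive on the plasma screen, and that early termination means stopping ganaxolone.

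Two stronger readings should be resisted. One is that the rule biases or depletes the primary analysis; the timing of the screen and SAP Section 4.2.1.1 rule that out as a claim. The other is that the sponsor means to remove patients on approved CBD; Section 5.4 points the other way. The documents do not define the Part A completion status of a patient terminated at Visit 5, and nothing is claimed about it.

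**What to change.** Replace the last sentence of Table 1 footnote h with:

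> A positive test for THC, or for CBD without a prescription for an approved CBD, during the 12-week treatment period of Part A (after the first dose of GNX) will result in early termination.

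Use the same sentence in Section 7.4.2 for consistency, and let the SAP Appendix A copy follow the protocol.

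The time limit should not be shortened to Part A alone. Part A includes the four-week baseline that starts at Visit 1, so the shorter wording would terminate a patient for a positive screening test that footnote h and Sections 7.2.1.1 and 7.4.2 allow to be retested after two weeks. Naming the 12-week period also makes clear that the rule does not extend to the Week 28 screen in Part B, where Section 5.4 permits these products.

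The cost is one sentence in the protocol footnote, the matching sentence in Section 7.4.2 and the SAP reproduction. No test, data item or analysis changes.

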k.	Concomitant AEDs or their dose must be stable for 1 month prior to screening and cannot be changed at any time prior to Visit 4, but may be adjusted during Part B.										
l.	Caregiver given seizure and medication diary and instructions for use.										
m.	During the baseline visit, the investigator and parent/caregiver/LAR will decide on a domain and identify the specific behavior that the patient exhibits that denotes the domain. This behavior will be used at subsequent visits to assess change after the initiation of IP.										
n.	Patients who discontinue IP early will be encouraged to continue with all procedures and scheduled visits.										
o.	The 4 weeks between Screening Visit and Baseline Treatment Visit can be no less than 28 days and no more than 32 days.										
p.	Only for patients who do not continue into Part B. This will occur after 2 weeks of taper and 2 weeks after completion of treatment.										
q.	Only for patients \geq 7 years old if appropriate. Otherwise clinical judgment will be used.										
r.	Only for patients that were Screened without previous genetic testing results and had a genetic test performed at the sponsor's designated lab.										

Table 1: Schedule of Assessments - Part A

WEEK	Part A										
	Screen/Baseline		Titration and Maintenance								
-4 (Screening Visit – Start of Baseline)	0 (Baseline Treatment Visit)	Day 1	Day 2	Day 3	1	2, 3, 4	5	9	12	16 Taper/Safety Visits ^p	
Visit Windows	+ 4 days			± 1 day	± 3 days	± 3 days	± 3 days	± 3 days	± 3 days	± 3 days	
VISIT	Visit 1 ^a	Visit 2 ^o	Phone Follow-up	Phone Follow-up	Phone Follow-up	Visit 3	Phone Follow-up	Visit 4	Phone Follow-up	Visit 5	Visit 5a

s. Review of medical history only.

t. Developmental examination is limited to pediatric patients 2 to 17 years of age, inclusive.

Table 2: Schedule of Assessments - Part B

Part B								
	Final Part A Visit/ First Part B Visit	Open-Label Extension (Visits will be every 8 weeks with a telephone follow-up in-between)					Final OLE Visit or Taper Visit	Safety Follow-up Post-taper
WEEK	12	16	20	24	28	32	36 or early D/C	2 weeks post last dose
Visit Windows		± 7 days	± 7 days	± 7 days	± 7 days	± 7 days	± 7 days	± 3 days
VISIT	Visit 5	Phone follow-up	Visit 6	Phone follow-up	Visit 7	Phone follow-up	Visit 8 (Week 36) ^g or Visit X (early D/C)	Visit X
Confirm patient is “OLE eligible” (≥ 35% reduction in seizure frequency)	X							
Vital signs (BP, HR, RR, and body temperature)	X		X		X		X	X

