3. STUDY DESIGN

3.1. Study Design and Flow Chart

This is an OL proof of concept study of adjunctive GNX treatment in patients with a confirmed clinical diagnosis of TSC and/or a mutation in either the *TSC1* or *TSC2* gene. The trial consists of two parts: Part A consists of a 4-week baseline period followed by a 12-week treatment period (4-week titration and 8-week maintenance). For patients not continuing in the OLE period (Part B), a 2-week taper period followed by a 2-week safety period would follow. The main difference between Part A and Part B is the length of treatment, less frequent assessments, and the ability to alter drug doses (both GNX and other AED treatments which includes initiating and stopping other medications) based on investigator evaluation of the patient's clinical course during Part B. Patients with a seizure frequency reduction rate of $\geq 35\%$ during the 12-week treatment period in Part A compared to baseline may continue into Part B ("OLE eligible"). If the investigator believes there is a medical benefit for the patient who does not meet the seizure reduction criterion to enter the OLE, they must discuss the patient with the sponsor medical monitor and receive sponsor approval for that patient to continue into the OLE.

Part A

- 4-week baseline period

[figure not shown]
IND 044,020
Protocol 1042-TSC-2001Marinus Pharmaceuticals, Inc.
11 Jun 2021

- 4-week titration period
- 8-week maintenance period
- 2-week taper period (For patients who do not complete Part A or after completing Part A but do not continue into Part B)
- 2-week safety follow-up visit post taper (For patients who taper off GNX)

Part B (Optional for OLE-eligible patients)

- OLE period (until the Sponsor markets ganaxolone or terminates the study)
- 2-week taper period (For patients who discontinue GNX due to early termination or completion)
- 2-week safety follow-up visit post-taper (For patients who taper off GNX)

Figure 1: Study Design

GNX = ganaxolone

During the screening visit, each patient's baseline [REDACTED] will be collected and analyzed for post-study evaluation.

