5. Have at least 8 countable/witnessed primary seizures during the 4-week baseline period with at least 1 primary seizure occurring in at least 3 of the 4 weeks of baseline. The primary seizure types are defined as the following: focal motor seizures without impairment of consciousness or awareness, focal seizures with impairment of consciousness or awareness, focal seizures evolving to bilateral, tonic-clonic convulsive seizures, and generalized motor seizures including tonic-clonic, bilateral tonic, bilateral clonic, or atonic/drop seizures. Focal aware non-motor and generalized seizures without motor features, infantile or epileptic spasms, and myoclonic seizures do not count as the primary seizure types.
6. Patient must be approved to participate by the sponsor or its designee (e.g., Epilepsy Consortium) after review of medical history, genetic testing, and patients' seizure types.

7. Patients should be on a stable regimen of ASMs at therapeutic doses for \geq 1 month prior to the screening visit, without a foreseeable change in dosing for the duration of Part A. Vagus nerve stimulator (VNS), ketogenic diet, and modified Atkins diet should be unchanged for 3 months prior to screening and will not count towards the number of ASMs.
8. Patients with surgically implanted VNS will be allowed to enter the study provided that all of the following conditions are met:
 - a. The VNS has been in place for \geq 1 year prior to the screening visit.
 - b. The settings must have remained constant for 3 months prior to the screening visit and remain constant throughout the baseline and Part A.
 - c. The battery is expected to last for the duration of baseline and Part A.
9. Parent/caregiver is able and willing to maintain an accurate and complete daily seizure diary for the duration of the study.
10. Able and willing to take IP (suspension) with food 3 times daily. (GNX must be administered with food).

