7.2.5. Titration Period (Phone Follow-ups, Weeks 2, 3, and 4 ± 3 days)

A telephone follow-up visit will be conducted at Weeks 2, 3, and 4 (\pm 3 days) to assess the following:

- AEs
- Seizure and medication diary review

7.2.6. Maintenance Period (Visits 4 and 5, Weeks 5 and 12 ± 3 days)

The following study procedures/assessments will be completed at Weeks 5 and 12 (\pm 3 days):

- Vital signs (to include BP, HR, RR, and body temperature)
- Weight
- Physical, neurological, and developmental examination (developmental examination is limited to pediatric patients 2 to 17 years of age, inclusive)
- ECG
- Clinical laboratory tests (chemistry and hematology)
- Urinalysis
- Drug screen (plasma) for THC and CBD (Visit 5 [Week 12])
- Serum pregnancy test for all girls/women of childbearing potential
- IP PK sample (Visit 4 [Week 5], between 1-5 hours after last IP dose and Visit 5 [Week 12], between 4-8 hours after last IP dose)
- Concomitant AED review and levels if per standard of care
- [REDACTED]
- AEs
- Seizure and medication diary review
- [REDACTED]
- CGI-C (parent/caregiver/LAR identified behavioral target)
- CGI-I (parent/caregiver/LAR and clinician)
- C-SSRS (since previous visit). Only for patients \geq 7 years old if appropriate, otherwise clinical judgement will be used.

- Dispense IP

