7.2.7. Maintenance Period (Phone Follow-up, Week 9 ± 3 days)

A telephone follow-up visit will be conducted at Week 9 (\pm 3 days) to assess the following:

- AEs
- Seizure and medication diary review

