1 INTRODUCTION

This statistical analysis plan (SAP) provides details and specifications for the statistical analyses of data collected under Marinus Pharmaceuticals, Inc. Protocol 1042-SC-2001, “A Phase 2 Open-label 12-Week Trial of Adjunctive Ganaxolone Treatment (Part A) in Tuberous Sclerosis Complex-related Epilepsy followed by Long-term Treatment (Part B)” (Version 2, Protocol Amendment 1, 12 May 2020).

The structure and content of this SAP provide sufficient detail to meet the requirements identified by the US Food and Drug Administration (FDA) and International Conference on Harmonization (ICH) of Technical Requirements for Registration of Pharmaceuticals for Human Use: Guidance on Statistical Principles in Clinical Trials.¹ All work planned and reported for this SAP will follow internationally accepted guidelines for statistical practice published by the American Statistical Association².

The following documents were also considered in preparation in writing this SAP:

- ICH E3 Guideline: Structure and Content of Clinical Study Reports³
- ICH E6 Guideline: Good Clinical Practice⁴
- ICH E8: General Considerations for Clinical Trial⁵
- ICH E9: Statistical Principles for Clinical Trials⁶

The SAP is a supplement to the study protocol which should be references for additional details on study design, study conduct, and other operational aspects of the study.

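### Footnote k of the Part A schedule stops barring concomitant AED changes at Visit 4 (Week 5), but Protocol Section 5.2.1 bars them until Visit 5 (Week 12)

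*Protocol*

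**What the plan says.** Protocol Table 1 attaches footnote k to the concomitant AED review row. After requiring one month of stability before screening, it says that AEDs or their dose "cannot be changed at any time prior to Visit 4, but may be adjusted during Part B". SAP Appendix A carries the same footnote.

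Protocol Section 5.2.1, the dedicated rule on concomitant AEDs, says that they "cannot be changed at any time prior to Visit 5 during Part A, but may be adjusted during Part B".

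Section 7.2.6 places Visit 4 at Week 5 and Visit 5 at Week 12, each ± 3 days. Section 7.3.1 makes Visit 5 the first visit of Part B. Section 3.1 names as a difference between the two parts "the ability to alter drug doses (both GNX and other AED treatments which includes initiating and stopping other medications", and ties it to Part B. The synopsis says the same, and both places also say that doses of other anti-seizure medications may be adjusted during Part B.

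**The concern.** The two sentences are nearly identical but name different visits, and both are current text. Footnote k sits on the row that a site consults when it reviews AEDs at a visit. Read alone, it states no prohibition after Week 5, whereas Section 5.2.1 prohibits changes for seven more weeks.

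This matters because the primary endpoint (Protocol Section 9.6.1) is the percent change in 28-day seizure frequency over 12 weeks against a 4-week baseline, with no control group. If another AED is added, stopped or re-dosed inside that window, nothing in the design separates its effect from that of ganaxolone. The same 12-week frequency feeds the 50% responder endpoint and the 35% criterion for entering Part B.

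The second consequence is for the PP set. SAP Section 2.2 leaves major violations to be defined before database lock, and the PP repeat is the only sensitivity analysis listed for the primary endpoint (SAP Section 4.2.1.2). With two freeze dates in force, it is unclear whether a change between Visits 4 and 5 is a violation at all.

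**Working it through.** The plan gives no figure of its own to reproduce here. The check has two parts: which visit is meant, and how long the disputed interval is.

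**Which visit is meant**

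| Place | What it implies for the end of the freeze |
|---|---|
| Table 1 footnote k, first half | Visit 4 |
| Table 1 footnote k, second half | Adjustment belongs to Part B, so Visit 5 |
| Section 5.2.1 | Visit 5 |
| Section 3.1 and synopsis | AED alteration is a Part B feature, so Visit 5 |
| Section 4.1, criterion 7: "without a foreseeable change in dosing for the duration of Part A" | End of Part A |
| Section 5.2.1, felbamate: "is expected to remain constant throughout the 12-week treatment period" | Week 12 |

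The last two rows are weaker evidence. They state what is expected at entry and do not prohibit changes on study. Without them, every other line still points to Visit 5, and only the visit number in the first half of footnote k disagrees.

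**How long the interval is**

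Inputs: Visit 4 at Week 5 = Day 35; Visit 5 at Week 12 = Day 84; ± 3 days at each visit; primary window 12 weeks = 84 days; maintenance period 8 weeks = 56 days.

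- Nominal gap: 84 − 35 = 49 days.
- Share of the primary window: 49/84 = 58%.
- Shortest gap, Visit 4 late and Visit 5 early: (81 − 38)/81 = 43/81 = 53%.
- Longest gap, Visit 4 early and Visit 5 late: (87 − 32)/87 = 55/87 = 63%.
- Share of the protocol's maintenance period: 49/56 = 88%.

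These figures measure how long the footnote is silent. They do not measure bias. The documents do not say how often AEDs change in Part A or how far a change moves seizure counts, so no bias can be computed from them.

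**The case against.** The strongest reply is that the protocol largely resolves the conflict itself. The second half of footnote k allows adjustment only in Part B, Section 5.2.1 is the governing rule, and the design section agrees with it. On this view the footnote is a one-digit slip. That stands as a description of how the error arose, and it limits the weight of the point. It does not remove the error, because the footnote's stated prohibition still ends seven weeks too early.

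Four stronger readings are tempting, and the documents do not support them.

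- *That the footnote permits AED changes from Week 5.* It does not. It leaves the interval between Visits 4 and 5 unaddressed.
- *That a change in the interval would go unseen.* The listed item "Concomitant AED review and levels if per standard of care" is scheduled at Visits 4 and 5 and not between them, and Section 7.2.7, which says that "A telephone follow-up visit will be conducted at Week 9", lists only adverse events and diary review. But Section 5 asks the investigator to assess all concomitant medications at every visit, although whether that covers telephone visits is arguable. Caregivers record non-study AEDs daily (Sections 6.5 and 7.5.1). Diary entries are due within 48 hours and are monitored (Section 9.1), and the diary is reviewed at Week 9. The SAP presents AEDs separately (Section 4.1.5) and lists violations (Section 4.1.2).
- *That the SAP contains a second, independent error.* SAP Section 1.3.1 says that its appendices reproduce the protocol schedule, and the SAP was written to "Version 2, Protocol Amendment 1, 12 May 2020". Its footnote is a copy.
- *That the intent-to-treat analysis is left undefined.* SAP Section 4.2.1.1 includes all available Part A seizure data, so data after an AED change are counted. Only the PP classification is open.

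**Conclusion.** This is an internal inconsistency, and footnote k is wrong as written. Visit 5 is the intended end of the freeze. The footnote omits the prohibition for 49 of the 84 primary-window days (58%; 53% to 63% across the visit windows).

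A reader might infer that the primary result is materially biased. The documents do not show that. The size of any effect is unknown. That it is probably small at group level is a judgement: it assumes that few of about 30 patients change an AED in the interval, given that they enter with no foreseeable change and that the text elsewhere confines adjustment to Part B. The case for correcting the footnote is that the endpoint is uncontrolled, the intended rule is clear and the correction is nearly free.

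**What to change.** In Protocol Table 1 footnote k, change Visit 4 to Visit 5, and let the copy in SAP Appendix A follow. When major violations are defined before database lock, state that the AED freeze ends at Visit 5, and exclude rescue medication, which Section 5.3 allows. Whether a particular AED change counts as major stays a judgement for that step.

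The cost is one visit number and one line in definitions still to be written. No new data are needed. The protocol change needs sponsor and IRB/EC approval (Section 10.3.2), so it can travel with the next amendment. If Part A treatment is largely finished by then, the line in the violation definitions is the part that still matters. The downside is that a patient whose AED was changed in good faith under footnote k would be judged against Visit 5 and could leave the PP set.
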